14.9 Appendix 9: ECG Findings of Potential Clinical Concern

ECG Findings That May Qualify as AEs

- Marked sinus bradycardia (rate <40 bpm) lasting minutes.
- New PR interval prolongation >280 msec.
- New prolongation of QTcF to >480 msec (absolute) or by 60 msec from baseline.
- New-onset atrial flutter or fibrillation, with controlled ventricular response rate: ie, rate <120 bpm.
- New-onset type I second-degree (Wenckebach) AV block of >30 seconds' duration.
- Frequent PVCs, triplets, or short intervals (<30 seconds) of consecutive ventricular complexes.

ECG Findings That May Qualify as Serious Adverse Events (SAEs)

- QTcF prolongation >500 msec.
- New ST-T changes suggestive of myocardial ischemia.
- New-onset left bundle branch block (QRS >120 msec).
- New-onset right bundle branch block (QRS >120 msec).
- Symptomatic bradycardia.
- Asystole:
 - In awake, symptom-free patients in sinus rhythm, with documented periods of asystole 3.0 seconds or any escape rate <40 bpm, or with an escape rhythm that is below the AV node;
 - In awake, symptom-free patients with atrial fibrillation and bradycardia with 1 or more pauses of at least 5 seconds or longer;
 - Atrial flutter or fibrillation, with rapid ventricular response rate: rapid = rate >120 bpm.
- Sustained supraventricular tachycardia (rate >120 bpm) ("sustained" = short duration with relevant symptoms or lasting >1 minute).

- Ventricular rhythms >30 seconds' duration, including idioventricular rhythm (heart rate <40 bpm), accelerated idioventricular rhythm (HR 40 bpm to <100 bpm), and monomorphic/polymorphic ventricular tachycardia (HR>100 bpm (such as torsades de pointes)).
- Type II second-degree (Mobitz II) AV block.
- Complete (third-degree) heart block.

ECG Findings That Qualify as SAEs

- Change in pattern suggestive of new myocardial infarction.
- Sustained ventricular tachyarrhythmias (>30 seconds' duration).
- Second- or third-degree AV block requiring pacemaker placement.
- Asystolic pauses requiring pacemaker placement.
- Atrial flutter or fibrillation with rapid ventricular response requiring cardioversion.
- Ventricular fibrillation/flutter.
- At the discretion of the investigator, any arrhythmia classified as an adverse experience.

The enumerated list of major events of potential clinical concern are recommended as "alerts" or notifications from the core ECG laboratory to the investigator and Pfizer study team, and not to be considered as all inclusive of what to be reported as AEs/SAEs.

14.10 Appendix 10: Alternative Measures During Public Emergencies

The alternative study measures described in this section are to be followed during public emergencies, including the COVID-19 pandemic. This appendix applies for the duration of the COVID-19 global pandemic and will become effective for other public emergencies only upon written notification from Pfizer.

Use of these alternative study measures are expected to cease upon the return of business as usual circumstances (including the lifting of any quarantines and travel bans/advisories).

14.10.1 Eligibility

Enrollment for this study was closed prior to the COVID-19 pandemic.

14.10.2 Telehealth Visits

In the event that in-clinic study visits cannot be conducted, every effort should be made to follow up on the safety of study patients at scheduled visits per the Visit Schedules and

Assessments ([Section 7](#), [Table 7-2](#)) or unscheduled visits. Telehealth visits may be used to continue to assess patient safety and collect data points. Telehealth includes the exchange of healthcare information and services via telecommunication technologies (e.g., audio, video, video-conferencing software) remotely, allowing the patient and the investigator to communicate on aspects of clinical care, including medical advice, reminders, education, and safety monitoring. The following assessments must be performed during a telehealth visit:

- Review and record study treatment(s), including compliance and missed doses.
- Review and record any AEs and SAEs since the last contact. Refer to [Section 8.1](#).
- Review and record any new concomitant medications or changes in concomitant medications since the last contact.
- Review and record contraceptive method and results of pregnancy testing. Confirm that the patient is adhering to the contraception method(s) required in the protocol. Refer to [Section 7.2.2.5.5](#) and [Section 14.10.3.1](#) of this appendix regarding pregnancy tests.

Study patients must be reminded to promptly notify site staff about any change in their health

14.10.3 Alternative Facilities for Safety Assessments

14.10.3.1 Laboratory Testing

If a study patient is unable to visit the site for protocol-specified safety laboratory evaluations, testing may be conducted at a local laboratory if permitted by local regulations. The local laboratory may be a standalone institution or within a hospital. The following safety laboratory evaluations may be performed at a local laboratory:

- Refer to [Section 7.2.2.5](#) for the list of safety laboratory evaluations, including pregnancy testing, required per protocol.

If a local laboratory is used, qualified study site personnel must order, receive, and review results. Site staff must collect the local laboratory reference ranges and certifications/accreditations for filing at the site. Laboratory test results are to be provided to the site staff as soon as possible. The local laboratory reports should be filed in the patient's source documents/medical records. Relevant data from the local laboratory report should be recorded on the CRF.

If a patient requiring pregnancy testing cannot visit a local laboratory for pregnancy testing, a home urine pregnancy testing kit with a sensitivity of at least 25 IU/mL may be used by the patient to perform the test at home, if compliant with local regulatory requirements. The pregnancy test outcome should be documented in the patient's source documents/medical records and relevant data recorded on the CRF. Confirm that the patient is adhering to the contraception method(s) required in the protocol.

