At this stage of the trial, the safety and efficacy of the dual combination of LGX818/MEK162 and the triple combination of LGX818/MEK162/LEE011 have been thoroughly assessed. Therefore, Amendment 10 allows for patients still on treatment to be monitored in a manner that is consistent with local standard-of-care practice. In addition, post-treatment disease progression follow-up (if applicable) and/or survival follow-up (including documentation of subsequent antineoplastic therapies) will no longer be performed for patients in the Phase II part of the study.

As of the date of this amendment, 10 patients are still on study treatment, with 5 patients receiving the dual combination (LGX818/MEK162) and 5 patients receiving the triple combination (LGX818/MEK162/LEE011). In addition, 20 patients enrolled in the Phase II part of the study who have discontinued study treatment are still in the disease progression/survival follow-up period, with 12 patients who had received the dual combination (LGX818/MEK162) and 8 patients who had received the triple combination (LGX818/MEK162/LEE011).

The purpose of this amendment is to:

1. To modify the frequency of assessments to allow for patients still on treatment to be monitored in a manner that is consistent with local standard-of-care practice.
2. To discontinue post-treatment disease progression follow-up (if applicable) and/or survival follow-up (including documentation of subsequent antineoplastic therapies) for patients in the Phase II part of the study.
3. To revise the Adverse Event and Serious Adverse Events sections to align with Pfizer standard operating procedures, with SAE reporting directly to Pfizer Safety;
4. To reflect the dose modification and management related to MEK162- and LEE011-emerging ILD/pneumonitis and LEE011-emerging Toxic Epidermal Necrolysis (TEN);

Changes to the Protocol

Changes to specific sections of the protocol are shown in the track changes version of the protocol.

Section 1.2

- Section 1.2.1: addition of nomenclatures used for LGX818;
- Section 1.2.2: addition of nomenclatures used for MEK162;

- Section 1.2.3: addition of nomenclatures used for LEE01 1 and references to the cmTent LEE01 1 Investigator's Brochure.

Section 4

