 - For addition of LEE011 in the triple combination, congenital long QT syndrome or family history of unexpected sudden cardiac death.
 - For addition of LEE011 in the triple combination, any heart disease that requires the use of a cardiac pacemaker or implantable cardioverter defibrillator ≤ 3 months prior to starting study drug or any other clinically significant heart disease (e.g. documented congestive heart failure, documented cardiomyopathy).
7. Patients with any of the following laboratory values at Screening/baseline:
 - Absolute neutrophil count (ANC) < 1,500/mm³ [1.5 x 10⁹/L]
 - Platelets < 100,000/mm³ [100 x 10⁹/L]
 - Hemoglobin < 9.0 g/dL
 - Serum creatinine > 1.5 x ULN or calculated or directly measured CrCl < 50% LLN (lower limit of normal)
 - Serum total bilirubin > 1.5 x ULN

- AST/SGOT and/or ALT/SGPT > 2.5 x ULN, or > 5 x ULN if liver metastases are present
 - For addition of LEE011 in the triple combination, serum magnesium, potassium, sodium, inorganic phosphate and calcium (corrected for serum albumin) < LLN or not correctable with supplement to within normal limits prior to study treatment start, and PT/INR >1.5 x ULN or aPTT >1.5 x ULN
8. Impairment of gastrointestinal (GI) function or GI disease that may significantly alter the absorption of oral LGX818, MEK162 or LEE011 (e.g., ulcerative diseases, uncontrolled nausea, vomiting, diarrhea, malabsorption syndrome, small bowel resection).
9. Previous or concurrent malignancy. Exceptions: adequately treated basal cell or squamous cell skin cancer; in situ carcinoma of the cervix, treated curatively and without evidence of recurrence for at least 3 years prior to study entry; or other solid tumor treated curatively, and without evidence of recurrence for at least 3 years prior to study entry.
10. Pregnant or nursing (lactating) women, where pregnancy is defined as the state of a female after conception and until the termination of gestation, confirmed by a positive hCG laboratory test (> 5 mIU/mL).

Women of child-bearing potential, defined as all women physiologically capable of becoming pregnant, are not allowed to participate in this study UNLESS they are using highly effective methods of contraception throughout the study and for 3 months after study drug discontinuation. Highly effective contraception methods include:

- Total abstinence or
- Male or female sterilization
- Combination of any two of the following (a+b or a+c or b+c)

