 - a. Use of oral, injected, or implanted hormonal methods of contraception
 - b. Placement of an intrauterine device (IUD) or intrauterine system (IUS)
 - c. Barrier methods of contraception: condom or occlusive cap (diaphragm or cervical/vault caps) with spermicidal foam/gel/film/cream/vaginal suppository

Post-menopausal women are allowed to participate in this study. Women are considered post-menopausal and not of child bearing potential if they have had 12 months of natural (spontaneous) amenorrhea with an appropriate clinical profile (e.g. age appropriate, history of vasomotor symptoms) or six months of spontaneous amenorrhea with serum Follicle-Stimulating Hormone (FSH) levels > 40 mIU/mL or have had surgical bilateral oophorectomy (with or without hysterectomy) or tubal ligation at least six weeks prior to screening. In the case of oophorectomy alone, only when the reproductive status of the woman has been confirmed by follow-up hormone level assessment is she considered not of child bearing potential.

Sexually active males must use a condom during intercourse while taking the drug and for 5 T_{1/2} after stopping treatment and should not father a child in this period. A condom is required to be used also by vasectomized men in order to prevent delivery of the drug via seminal fluid.

11. History of thromboembolic or cerebrovascular events within the last 6 months, including transient ischemic attack, cerebrovascular accident, deep vein thrombosis, or pulmonary embolism.

12. Patients who have received radiation therapy (that includes > 30% of the bone marrow reserve), chemotherapy, biological therapy (e.g., antibodies) within ≤ 4 weeks (6 weeks for nitrosourea, mitomycin-C), or who have been treated with continuous or intermittent small molecule therapeutics or investigational agents within 5-half-lives of the agent (or ≤ 4 weeks when half-life is unknown) prior to starting study drug or who have not recovered from the side effects of such therapy (except alopecia).
13. Patients who have undergone any major surgery within the last 2 weeks prior to starting study drug or who would not have fully recovered from previous surgery.
14. Known Human Immunodeficiency Virus (HIV) infection.

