
^a. The minimally required procedures/assessments are indicated; these or any additional procedures/assessments can be repeated more frequently per standard-of-care or if clinically indicated.
 
^b. Following the 30-day Safety Follow-up, when clinically appropriate, it is recommended patients be monitored with physical examinations, dermatological examinations, and chest CT scans for cutaneous and non-cutaneous secondary malignancies for up to 6 months after the last LGX818 dose or until initiation of another antineoplastic therapy.
 
^c. To be conducted if clinically indicated.
 
^d. Local urine test for women of childbearing potential only.
 
^e. Assessed by ECHO or MUGA. The same method should be used throughout the study. Patients who develop signs/symptoms of CHF at any point during the study are required to have an evaluation by ECHO or MUGA.
 
^f. Patients who have been on the LGX818/MEK162 dual combination and LGX818/MEK162/LEE011 triple combination treatment for ≥ 24 months (Cycle 25 Day 1 onward) without a retinal AE should be evaluated for visual acuity per local standard-of-care (recommended every 4 weeks) and at the End of Treatment visit. A full ophthalmic examination is required if clinically indicated and at the End of Treatment visit.
 
^g. SEC eCRF should be completed once the 30-day safety follow-up period is completed or 30 days after treatment discontinuation.
							

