7.2.2.5.5 Pregnancy and assessments of fertility

All females of childbearing potential will have a serum pregnancy test ≤ 72 hrs before first dose of study drug and a urine or serum during study treatment (Day 1 of Cycle 2 and onwards) and at the End of Treatment visit.

A positive urine pregnancy test requires immediate interruption of study treatment until serum β -HCG is performed and found to be negative. If positive, the patient must be discontinued from the study.

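### Section 14.10.3.1 gives the home urine pregnancy kit's sensitivity limit in IU/mL, almost certainly in place of mIU/mL, a 1,000-fold unit error

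*Protocol*

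**What the plan says.** Appendix 10 of the Protocol sets fallback procedures: "The alternative study measures described in this section are to be followed during public emergencies". Within it, section 14.10.3.1 first moves safety laboratory work to a local laboratory. If a patient who needs pregnancy testing cannot get there either, "a home urine pregnancy testing kit with a sensitivity of at least 25 IU/mL may be used by the patient", provided local regulation allows it. That is the only performance requirement placed on the kit.

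Four other places bear on the figure:

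- Section 5.3, criterion 10, defines pregnancy as "confirmed by a positive hCG laboratory test (> 5 mIU/mL").
- The same criterion supports one definition of post-menopausal status with "serum Follicle-Stimulating Hormone (FSH) levels > 40 mIU/mL".
- Section 7.2.2.5.5 states the consequence of a positive result on treatment: "A positive urine pregnancy test requires immediate interruption of study treatment until serum" β-HCG has been measured and is negative. If the serum test is positive, the patient is discontinued.
- Table 7-2, footnote d, makes the routine test from Amendment 10 onward a urine test: "Local urine test for women of childbearing potential only".

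The telehealth rules in section 14.10.2 require staff to "Review and record contraceptive method and results of pregnancy testing" and refer back to 14.10.3.1. The home health rules in section 14.10.4 do the same.

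**The concern.** The kit limit is the only hormone threshold in the protocol expressed in IU/mL. Read as written, it lies far above the level at which the protocol itself calls a laboratory test positive, so it does not work as a minimum standard for a pregnancy test.

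The urine result is a trigger. A positive result interrupts treatment and leads to serum confirmation, and the reporting of exposure during pregnancy (section 8.1.5.1) also depends on the pregnancy being detected. For a woman who can reach neither the site nor a laboratory, the home kit is the pregnancy test the appendix provides. Section 14.10.3.4 allows study drug to be couriered to her, so dosing can continue meanwhile. A kit that met only the literal limit might not trigger any of these steps.

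**Working it through.** The 25 IU/mL is a specification. It is not derived from other inputs, so there is no calculation in the plan to reproduce. The check is a unit conversion followed by a comparison with the protocol's other thresholds.

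**Inputs**

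| Quantity | Value | Source |
|---|---|---|
| Home kit limit as written | 25 IU/mL | 14.10.3.1 |
| Laboratory hCG cut-off for pregnancy | > 5 mIU/mL | 5.3, criterion 10 |
| FSH limit (unit comparison only) | > 40 mIU/mL | 5.3, criterion 10 |
| Presumed intended kit limit | 25 mIU/mL | Inference; not stated in the protocol |

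**Conversion.** 1 IU = 1,000 mIU, so 25 IU/mL × 1,000 = 25,000 mIU/mL.

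**Ratios**

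- Written limit against presumed limit: 25,000 / 25 = 1,000.
- Written limit against the protocol's laboratory cut-off: 25,000 / 5 = 5,000.
- Presumed limit against the laboratory cut-off: 25 / 5 = 5.

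The 5,000-fold figure uses only numbers stated in the protocol. The 1,000-fold figure also needs the inference that mIU/mL was meant.

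**Search for a correcting value.** Section 7.2.2.5.5, Table 7-2 footnote d, and sections 14.10.2 and 14.10.4 all deal with pregnancy testing, and none gives a kit sensitivity. The last two refer the reader to 14.10.3.1, so its figure governs both telehealth and home health visits.

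**Direction.** The phrase "a home urine pregnancy testing kit with a sensitivity of at least 25 IU/mL may be used by the patient" can be read two ways. If it means at least as sensitive as a 25 IU/mL kit, better kits comply and so does a very poor one. If it is read as a numerical floor on the detection limit, it would exclude the better kits. The first reading is the sensible one and is used here, but the sentence does not settle it.

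**Reach.** The protocol states: "As of the date of this amendment, 10 patients are still on study treatment". Section 14.10.1 says enrollment had already closed before the pandemic. The number of women of childbearing potential among the 10 is not given, so the affected group is between 0 and 10, and smaller still once limited to those who cannot reach a laboratory.

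**The case against.** The best opposing case accepts the conversion and argues that little harm could follow.

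- **Local regulation.** The sentence also requires home testing to comply with local rules, so 25 IU/mL is not the only constraint. Whether a lawful kit with a detection limit near 25,000 mIU/mL exists cannot be learned from the protocol. This stands, and it makes harm less likely.
- **Other safeguards.** Criterion 10 requires highly effective contraception. Section 6.4.2 requires at least one non-hormonal method, because LGX818 may weaken hormonal ones. Contraception is reviewed at telehealth and home health visits. Section 14.10.3.4 says discontinuation must be considered when missed evaluations put safety at risk. These stand as well, but they lower the chance of an unnoticed pregnancy without replacing a working test.
- **Inferred value.** The protocol nowhere states 25 mIU/mL. This is correct. What the protocol shows by itself is a unit out of line with criterion 10 and a limit 5,000 times its own cut-off.
- **Text extraction.** Characters are visibly lost elsewhere in the late appendices, so a dropped letter cannot be excluded. However, section 14.10.3.1 otherwise reads cleanly and mIU/mL came through intact in criterion 10. The sponsor can settle this by looking at the source file.
- **Weight.** This is a unit slip in a contingency appendix and not a miscalculation. That is fair, and it limits the importance of the point without making the figure right.

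**Conclusion.** The limit is wrong as written. It appears in operative safety text, it is the only sensitivity standard for the home kit, and it errs in the unsafe direction: 25,000 mIU/mL, 5,000 times the protocol's laboratory cut-off and 1,000 times the presumed intended value. The 1,000-fold figure assumes that 25 mIU/mL was meant, which the units in criterion 10 support strongly but do not prove. Any harm assumes that a kit close to the literal limit could lawfully be obtained and would be chosen.

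Practical importance is low. At most 10 patients were on treatment at Amendment 10, only women of childbearing potential without laboratory access during a public emergency are concerned, and kits more sensitive than the literal limit also comply. No efficacy or safety analysis changes.

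**What to change.** In section 14.10.3.1, replace the sensitivity wording with: *that detects hCG at 25 mIU/mL or lower*. This corrects the unit and removes the doubt about direction. The home kit need not match the 5 mIU/mL laboratory cut-off in criterion 10, because section 7.2.2.5.5 already sends a positive urine result to serum confirmation. The sponsor should confirm that 25 mIU/mL is the intended figure.

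The cost is one phrase in the next amendment or clarification letter, with no added procedure, visit or data collection.

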14.10.3.2 Imaging

If the patient is unable to visit the study site for safety imaging assessments (e.g., ECHO or MUGA), the patient may visit an alternative facility to have the safety imaging assessments performed. Qualified study site personnel must order, receive, and review results.

14.10.3.3 Electrocardiograms

If the patient is unable to visit the study site for ECGs, the patient may visit an alternative facility to have the ECGs performed. Qualified study site personnel must order, receive, and review results.

14.10.3.4 Study Treatment

If the safety of a trial patient is at risk because they cannot complete required evaluations or adhere to critical mitigation steps, then discontinuing that patient from study treatment must be considered.

Study drugs may be shipped by courier to study patients if permitted by local regulations and in accordance with storage and transportation requirements for the study drugs. Pfizer does not permit the shipment of study drugs by mail. The tracking record of shipments and the chain of custody of study drugs must be kept in the patient's source documents/medical records.

The following is recommended for the administration of study drugs for patients who have active [confirmed (positive by regulatory authority-approved test) or presumed (test pending/clinical suspicion)] SARS-CoV2 infection:

- For symptomatic patients with active SARS-CoV2 infection, study drugs should be delayed for at least 14 days from the start of symptoms. This delay is intended to allow the resolution of symptoms of SARS-CoV2 infection.
- Prior to restarting treatment, the patient should be afebrile for 72 hours, and SARS-CoV2-related symptoms should have recovered to \leq Grade 1 for a minimum of 72 hours. Notify the study team when treatment is restarted.
- Continue to consider potential drug-drug interactions as described in protocol [Section 6.4](#) for any concomitant medication administered for treatment of SARS-CoV2 infection.

